10.3.7 Optional Visit 10A, 10B: G100 Doses # 7, 8 (Days 42, 49)

For patients in Parts 2 and 3 whose treated tumor has not regressed completely, dosing may continue for 3 additional weekly intratumoral treatments (9 total) with doses #7 and 8 given on these visits. Note that on each immunization day, all procedures and blood draws must be done before dosing. The following will be completed:

- 1) Review of AEs and SAEs
- 2) Recording of any previous / concomitant medications
- 3) Vital signs
- 4) Symptom-directed physical exam

- 5) Assessment and measurements of tumor treated with G100 and measureable untreated distal tumor lesions by exam
- 6) ECOG status
- 7) Safety labs as in [Section 10.3.2 – Hematology, Clinical chemistry](#)
- 8) Optional G100 administration of Doses #7, 8 in qualified patients. (Note: If the tumor regressed and is no longer of sufficient size for injection per evaluation by the investigator and there are no alternate lesions within the irradiated area, the remaining G100 treatments and treatment visits may be cancelled. The patient should then continue with Clinical Assessment visits beginning on Day 56)

10.3.8 Visit 11: Clinical Assessment and Optional G100 Dose # 9 (Day 56)

This is a mandatory Clinical Assessment visit. For patients whose treated tumor has not regressed completely, 3 optional treatments may continue and the final dose #9 may be given on this visit. Note that on each immunization day, all procedures and blood draws must be done before dosing. The following will be completed:

- 1) Review of AEs and SAEs
- 2) Recording of any previous / concomitant medications
- 3) Vital signs
- 4) Symptom-directed physical exam
- 5) Assessment and measurements of tumor treated with G100 and measureable untreated distal tumor lesions by exam
- 6) ECOG status
- 7) Safety labs as in [Section 10.3.2 – Hematology, Clinical chemistry](#)
- 8) For patients in Part 1 and Part 2, blood for cell phenotyping / profiling (not collected in Part 3)
- 9) Blood for T cell gene profiling
- 10) For patients in the UK, urine pregnancy test
- 11) Assessment of disease including CT or MRI of chest, abdomen, pelvis. Other assessments such as CT of the head, body PET CT, or bone marrow biopsy should be performed if indicated. Day 56 (+/- 7 days) restaging CT or MRI scans should be performed if the optional treatment #9 is not given. If the 9th dose is given, then imaging studies should be delayed to Day 63 to 77. If a PET CT is used, a standard high resolution CT series should be obtained rather than low resolution scans for tumor measurements. However, PET scans should not be used to determine disease progression since it is expected that PET avidity will increase with the type of inflammation induced by this treatment and may lead to false positive results.

- 12) Photographs: if the tumor can be measured and assessed visually, photographic documentation with measurements should be considered in order to keep a record and help assess any response to treatment (may be performed at any time during study)
- 13) Post Treatment tumor biopsy. Post-treatment tumor biopsy of available tumor (treated or untreated tumor to investigate systemic response) should be performed on Day 56 +/- 1 week for patients not receiving optional treatment #9. If the 9th dose is given, then the biopsy should be delayed to Day 63 to 77. The biopsies should be performed on the treated tumor if feasible; if not available, a different site should be chosen. The location from where the sample was obtained (treated, non-treated, irradiated or non-irradiated, untreated distal site) must be recorded.
- 14) Optional G100 administration of Dose #9 in qualified patients

10.3.9 Visit 12: Post-Immunization / End of Study Visit (Day 77)

The following will be completed:

- 1) Review of AEs and SAEs (Note: Patients should have all AEs reported for at least 30 days following the last dose of the G100 study agent. This includes those who withdraw early before completion of the study.)
- 2) Recording of any previous / concomitant medications
- 3) Vital signs
- 4) Symptom-directed physical exam
- 5) Assessment and measurements of tumor treated with G100 and measureable untreated distal tumor lesions by exam
- 6) ECOG status
- 7) Safety labs as in [Section 10.3.2 – Hematology, Clinical chemistry](#)
- 8) 12-lead ECG
- 9) Urine pregnancy test for FCBP. (Serum pregnancy test may be performed for any urine pregnancy assay if site SOP allows this test.)
- 10) If the optional 9th dose was given, then imaging studies should be delayed to Day 63 to 77. Assessment of disease including CT or MRI of chest, abdomen, and pelvis should be performed. Other assessments such as CT of the head, body PET CT, or bone marrow biopsy should be completed if indicated. If a PET CT is used, a standard high resolution CT series should be obtained rather than low resolution scans for tumor measurements. However, PET scans should not be used to determine disease progression since it is expected that PET avidity will increase with the type of inflammation induced by this treatment and may lead to false positive results.

- 11) Photographs: if the tumor can be measured and assessed visually, photographic documentation with measurements should be considered in order to keep a record and help assess any response to treatment (may be performed at any time during study)
- 12) If the optional 9th dose was given, then the post-treatment tumor biopsy of available tumor (treated or untreated tumor to investigate systemic response) should be performed Day 63 to 77. The biopsies should be performed on the treated tumor if feasible; if not available, a different site should be chosen. The location from where the sample was obtained (treated, non-treated, irradiated or non-irradiated, untreated distal site) must be recorded.

10.3.10 Long-Term Follow-up Visits

10.3.10.1 Visits Before Disease Progression (Day 112, then every 8 weeks)

- 1) Any SAE that comes to the attention of the site staff that may be causally related to study drug must be reported to Immune Design regardless of time elapsed.
- 2) Recording of any previous / concomitant medications.
- 3) Vital signs
- 4) Symptom-directed physical examination
- 5) Assessment and measurements of tumor treated with G100 and measureable untreated distal tumor lesions by exam
- 6) ECOG performance status
- 7) Assessment of disease including CT or MRI (chest, abdomen, pelvis) (to be repeated 4 weeks later to confirm disease progression as defined by irRC). Other assessments such as a CT of head, body PET CT, or bone marrow biopsy should be performed if indicated. If a PET CT is used, a standard high resolution CT series should be obtained rather than low resolution scans for tumor measurements. However, PET scans should not be used to determine disease progression since it is expected that PET avidity will increase with the type of inflammation induced by this treatment and may lead to false positive results. Imaging studies will occur on Day 112, every 8 weeks thereafter for the first year, every 3 to 4 months for the second year, and then at least every 6 months for the third and subsequent years.
- 8) Photographs: if the tumor can be measured and assessed visually, photographic documentation with measurements should be considered in order to keep a record and help assess any response to treatment (may be performed at any time during study)
- 9) Safety labs as in [Section 10.3.2](#)– Hematology, Clinical chemistry

10.3.10.2 After Disease Progression (Every 8 to 12 Weeks)

Patients will receive telephone follow-up or clinic visit every 8 to 12 weeks after disease progression until 1 year after first study injection. Follow-up will include vital status (survival status), cancer status, and post-treatment anti-cancer therapy including time to next treatment, treatment details, and clinical response. If the patient agrees, the site may periodically

Immune Design

G100 (GLA-SE) and Pembrolizumab or Rituximab

Protocol IMDZ-G142; Version 04B, November 15, 2018

(e.g., every 2 to 4 months) contact the patient beyond 1 year to check on vital and cancer status (e.g., lymphoma transformation). In addition, any SAE and that comes to the attention of the site staff that may be causally related to study drug must be reported to Immune Design, regardless of time elapsed.

Note: Sections 10.3.11 to [10.3.15](#) apply only to patients randomized to receive pembrolizumab on Part 2, Patient Expansion With Or Without Pembrolizumab

10.3.11 Visits 7, 8, 9, 10: G100 Doses #3, 4, 5, 6 (Days 14, 21, 28, 35)

Patients will return for their G100 doses #3, 4, 5, and 6. Note that on each immunization day, all procedures and blood draws must be done before dosing. The following will be completed:

- 1) Review of AEs and SAEs
- 2) Recording of any previous / concomitant medications
- 3) Vital signs
- 4) Symptom-directed physical exam
- 5) Assessment and measurements of tumor treated with G100 and measureable untreated distal tumor lesions by exam
- 6) ECOG status
- 7) Safety labs as in [Section 10.3.2](#)– Hematology, Clinical chemistry
- 8) On Day 35, Visit 10 only, blood for cell phenotyping / profiling and for T cell gene profiling
- 9) G100 administration (Note: If the tumor regressed and is no longer of sufficient size for injection per evaluation by the investigator and there are no alternate lesions within the irradiated area, the remaining G100 treatments and G100 only treatment visits may be cancelled. The patient should then continue with pembrolizumab and Clinical Assessment visits)
- 10) Urine pregnancy test on Day 14 prior to pembrolizumab. Note: For patients in the UK and France, urine pregnancy tests must also be performed every month or sooner while the patient is receiving G100 and/or pembrolizumab.
- 11) On Day 14 and 35, administer pembrolizumab

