--	--

Immune Design**G100 (GLA-SE) and Pembrolizumab or Rituximab****Protocol IMDZ-G142; Version 04B; November 15, 2018**

	
During Part 2 and based on the continuous review of safety events, if the dose of 10 µg G100 is used during Patient Expansion and subsequently determined to have an increased safety risk, the DMC may recommend and the Sponsor may choose to reduce the dose of G100 to 5 µg or they may recommend stopping the G100 treatment. If the 5 µg dose level is determined not to be safe by the independent DMC, treatment with G100 will be stopped. Following evaluation by the DMC and the Sponsor, a further modification to the dose/treatment schedule could be recommended.
 
During Part 4 and based on the continuous review of safety events, if the dose of 20 µg/lesion G100 plus pembrolizumab is subsequently determined to have an increased safety risk, the DMC may recommend and the Sponsor may choose to reduce the dose of G100 to 10µg or they may recommend stopping the G100 treatment.
 
Similarly during Part 5, if G100 plus rituximab is subsequently determined to have an increased safety risk, the DMC may recommend and the Sponsor may choose to reduce the dose of G100 or they may recommend stopping the G100 treatment. As described in the Part 5 design, an optional cohort may be examined where the dose level associated with a DLT is split in two lesions in order to help determine if the lack of tolerability of the dose was due to the treatment of a single lesion or was limited due to the total systemic G100 exposure. Following evaluation by the DMC and the Sponsor, a further modification to the dose/treatment schedule could be recommended.
 
All patients treated with one or more injections of G100 will be considered part of the safety data set. Patients will be followed every 8 weeks until disease progression as defined by the irRC. Patients with disease progression by irRC (or symptomatic deterioration) will be followed thereafter every 8-12 weeks by telephone or clinical visit for up to one year (or longer if the patient agrees) after first study injection as long as they are able to engage in follow-up. Follow-up will ascertain vital status (survival status) as well as cancer status (e.g., lymphoma transformation), post-treatment anti-cancer therapy (including time to next treatment, treatment details, and clinical response), and any SAE that might be possibly related to G100 treatment. Patients followed on this study have developed delayed objective tumor responses occurring >18 months from study start. If patients develop late responses after initial IrRC progression but have not received additional therapy, they may be asked to consent to additional follow-up of clinical response and biomarker analyses.

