10.3.22.2 Visits After Disease Progression (Every 8 to 12 Weeks)

Patients will receive telephone follow-up or clinic visit every 8 to 12 weeks after **confirmed** disease progression (or symptomatic deterioration with therapy) for at least 1 year after first study injection. Follow-up will include vital status (survival status), cancer status, and post-treatment anti-cancer therapy including time to next treatment, treatment details, and clinical response. If the patient agrees, the site may periodically (e.g., every 2 to 4 months) contact the patient beyond 1 year to check on vital and cancer status. Delayed objective responses have been observed on this study at >18 months from Day 0. Therefore, if the patient should experience a clinical regression and has not received any additional therapy, the patient may be asked for consent to collect clinical information such as imaging studies and biomarkers.

Any SAE that comes to the attention of the site staff that may be causally related to G100 must be reported to Immune Design, regardless of time elapsed. All AEs experienced from the time of enrollment through 30 days following cessation of pembrolizumab (and/or G100, whichever is longer) treatment will be reported by the investigator. Any ECI experienced through 30 days following cessation of treatment should be reported within 24 hours to the Sponsor. Any SAE due to any cause other than progression of the cancer under study that occurs through 90 days following cessation of pembrolizumab treatment, or 30 days following cessation of treatment if the subject initiates new anticancer therapy, whichever is earlier, must be reported within 24 hours to the Sponsor. After the 90-day reporting period, any SAE that comes to the attention

of the site staff that may be causally related to pembrolizumab must be reported to Sponsor regardless of time elapsed.

Note: Sections 10.3.23 to [10.3.29.2](#) apply only to patients enrolled on Part 5, G100 Plus Rituximab

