### 5.6.5 Overall Survival (OS)

Overall Survival (OS) is defined as the time from date of first study treatment to death due to any cause. Overall survival in months is calculated as:  $(\text{date of death} - \text{date of first dose}) + 1) / 30.4375$ . Patients who are alive at the end of study will be censored at the last date the patient is known to be alive or data analysis cutoff date, whichever is earlier.

Summary of OS including median, 95% CI, 25th and 75th percentiles, and range will be estimated using the Kaplan-Meier method. The corresponding 95% CI for median will be calculated using the Brookmeyer and Crowley method. The Kaplan-Meier survival curve will be displayed.

OS data will be presented in a data listing.

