## **5.6.7 Time to Next Treatment and Duration of All Subsequent Therapies**

Time to next treatment is defined as the time from the date of first study treatment to the start date of subsequent therapy after PD. Patients who did not receive subsequent therapy after PD are censored at the date of last contact or death.

Duration of all subsequent therapies after PD in week is calculated as (date of subsequent therapies last administered – date of subsequent therapies first administered + 1)/7. If one patient has multiple consecutive systemic therapies, the duration will be summarized per patient. If the start and end dates of multiple systemic therapies overlap, then duration = (date of last systemic therapy last administered – date of first systemic therapy first administered + 1)/7.

Summary of time to next treatment including median, 95% CI, 25th and 75th percentiles, and range will be estimated using the Kaplan-Meier method. The corresponding 95% CI for median will be calculated using the Brookmeyer and Crowley method. Descriptive statistics using PROC UNIVARIATE of time to next treatment and duration of all subsequent therapies including only patients with subsequent anti-cancer therapies will also be reported.

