### Partial Dates for Subsequent Therapy

Incomplete subsequent therapy dates will be imputed. Imputed dates will be used to determine Study Day.

Partial start dates will be imputed as follows:

1. Only the year is reported, with month and day missing: If the subject's last study treatment and subsequent therapy are in the same year, then the date of the last dose of study treatment will be used to impute the start date of the subsequent therapy.
2. The month and year are reported, with day missing: The first day of the month will be used to impute the start of the subsequent therapy.

Partial end dates will be imputed for non-ongoing therapies as follows:

1. Only the year is reported, with month and day missing: the earlier of December 31 or analysis cut-off date will be used to impute the end of the therapy.
2. The month and year are reported, with day missing: The last day of the month will be used to impute the end of the therapy.

End dates for ongoing therapies will be imputed to analysis cut-off date.

If an imputation results in an imputed start date after the stop date, set the date with more imputation to the one with less imputation.

Subsequent anti-cancer therapies will be summarized by part, treatment and will be presented in a listing.

- Any subsequent anti-cancer therapy
- Type of therapy
- Subsequent systemic therapy regimen/agents
- Best response
- Reason for discontinuation

Subsequent procedures and surgeries will be presented in a separate listing.

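### OS and time to next treatment are at risk of upward bias after month 12, because required contact after progression stops 1 year after first injection while progression-free patients are followed on

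*Protocol*

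**What the plan says.** **After progression, Parts 1 to 3.** Protocol 10.3.10.2 reads: "Patients will receive telephone follow-up or clinic visit every 8 to 12 weeks after disease progression until 1 year after first study injection". Section 10.3.15.2 has the same rule for the Part 2 pembrolizumab arm. The required contact collects survival, cancer status and subsequent therapy, including time to next treatment. Beyond that year, if the patient agrees, the site may "contact the patient beyond 1 year to check on vital and cancer status"; subsequent therapy is not on that list. The synopsis (Safety Monitoring) and Section 4.7 say "for up to one year (or longer if the patient agrees) after first study injection as long as they are able to engage in follow-up".

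**After progression, Parts 4 and 5.** Sections 10.3.22.2 and 10.3.29.2 say "for at least 1 year after first study injection". The schedule footnotes for these Parts (Sections 3.5 and 3.6) still say until 1 year.

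**Without progression.** Visits continue every 8 weeks until irRC progression (Section 4.7), and imaging runs into the third and later years (for example 10.3.10.1).

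**SAP.** For OS (5.6.5): "Patients who are alive at the end of study will be censored at the last date the patient is known to be alive", or at the data cut-off if earlier. For TTNT (5.6.7) the event is the start of subsequent therapy after PD, and "Patients who did not receive subsequent therapy after PD are censored at the date of last contact or death". Both are estimated by Kaplan-Meier, with medians, quartiles and range. Under Partial Dates for Subsequent Therapy: "End dates for ongoing therapies will be imputed to analysis cut-off date". Protocol 14.3.3 lists OS and TTNT as exploratory analyses that may be done.

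**The concern.** Kaplan-Meier assumes that patients censored at a given time have the same later risk as those still observed. Here the clock for required post-progression contact starts at first injection, not at progression. After month 12 the patients sure to be observed are those who have not progressed; progressed patients stay in only if they opt in or have some other reason for contact.

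For TTNT this goes to the definition. A patient must progress before the event can occur, so after month 12 required follow-up covers mainly people who cannot yet have it. For OS the problem arises only if death is more likely after progression than before.

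At stake are the later parts of both curves and the medians and upper quantiles the SAP plans to report. A long or unreached median TTNT could partly reflect events that nobody was required to record. The cut-off rule for ongoing therapy has a related fault: it counts time on therapy after contact may have ceased.

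**Working it through.** The documents give no expected OS or TTNT figure, so there is none to reproduce. The check asks what the SAP's censoring rules return when the answer is known.

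**1. Hand check, ignoring death.** Assumptions, none from the documents: exponential time to progression with median 12 months, rate a = ln 2 / 12 = 0.0578 per month; mean 4 months from PD to next therapy, rate b = 0.25. The proportion free of next therapy is

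S(t) = (b·e^(−at) − a·e^(−bt)) / (b − a).

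- S(12) = (0.25 × 0.5 − 0.0578 × 0.0498) / 0.1922 = 0.635
- S(24) = (0.25 × 0.25 − 0.0578 × 0.0025) / 0.1922 = 0.324

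If progressed patients are lost at month 12, or at PD if later, nobody at risk after month 12 can have the event. The estimate stays at 63.5%, an excess of 63.5 − 32.4 = 31.1 points at month 24.

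**2. Simulation with deaths.** Same rates, plus death hazards of 0.003 per month before PD and 0.02 after; cut-off uniform over 18 to 48 months; 400,000 patients per scenario; opt-in unrelated to outcome. The reference is Kaplan-Meier with full contact to cut-off under the SAP's own rules. At month 24:

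| Contact beyond month 12 after PD | TTNT (reference 34%) | Excess | OS (reference 78%) | Excess |
|---|---|---|---|---|
| None | 65% | 31 | 88% | 10 |
| None, but one month observed past PD | 56% | 22 | 87% | 9 |
| 50% opt in | 45% | 11 | 81% | 3 |
| 90% opt in | 36% | 2 | 78.5% | 0.5 |

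Median TTNT is about 17 months with full contact. It is not reached in row 1, about 33 months in row 2 and about 21 months in row 3. The direction is the same with median PFS of 9 or 18 months.

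**3. Different hazards.** Post-PD death hazards were also taken from the 5-year OS figures in Protocol Appendix D, as a guide only: −ln(0.78)/5 = 0.05 and −ln(0.53)/5 = 0.127 per year. Pre-PD hazard was 0.01 per year, median time to PD 6, 12 or 24 months, median PD to next therapy 6 months, cut-off at month 48. Excess at month 36:

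- No opt-in: OS 3.7 to 17.4 points, TTNT about 38 to 52.
- 50% opt-in: OS 0.5 to 3.2, TTNT about 4 to 14.
- 90% opt-in: at most 0.5 and 2.3.
- 100% opt-in: zero.
- Equal death hazards before and after PD (0.05 per year), no opt-in: OS 86.0% against 86.1%, so no bias; TTNT 74.9% against 23.4%.

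In every scenario the excess at month 12 is zero, given complete contact up to that point.

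**4. Ongoing therapy (constructed example).** Therapy starts at month 9, last contact is month 12, cut-off is month 36. The SAP rule records 36 − 9 = 27 months; 12 − 9 = 3 were observed.

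**The case against.** A reader might infer that contact ends at 1 year and that the curves are therefore biased. The documents do not support that. Contact may continue if the patient agrees, the Part 4 and 5 procedures make 1 year a minimum, and the synopsis entry on duration of participation gives about 1 year or longer after PD without tying it to first injection. Uptake is unknown, and at 90% the bias is slight.

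Nor does a patient who progresses after month 12 necessarily drop out of sight at once. irRC progression needs confirmation at least 4 weeks later but is dated to the assessment at which PD was initially documented (SAP 5.6.4); a biopsy is requested at progression (Protocol 10.4.9); pembrolizumab patients have 30-day AE and 90-day SAE windows after treatment stops; and some patients with PD may start a second G100 course. One month of such observation lowers the 24-month TTNT estimate from 65% to 56% and lets the median be reached. A completely flat curve is a limiting case, not a forecast.

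The stakes are also modest. Neither endpoint carries a decision rule, the SAP plans no 24-month rates for them, and with 12 patients per Part 2 arm and up to 25 in Part 3 sampling error is large.

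All of that stands as a limit on size and certainty. It does not remove the dependence of follow-up on progression. Optional contact does not list next therapy, so it can move the last-contact date forward without recording the event. The additional follow-up for late responders (synopsis, 10.3.22.2, 10.3.29.2) is offered to progressed patients who have had no further therapy, which selects patients free of the TTNT event. The simulated opt-in, unrelated to outcome and with next therapy always recorded, is favourable on both counts.

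**Conclusion.** The point holds as a risk, not as a demonstrated bias. In Parts 1 to 3 required contact after progression stops 1 year after first injection; in Parts 4 and 5 nothing is guaranteed beyond that year. The SAP has no rule for the resulting imbalance. TTNT beyond month 12 is exposed by its definition; OS is exposed only if the death hazard rises after PD.

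Under the stated assumptions the 24-month excess runs from about 31 points (TTNT) and 10 (OS) with no opt-in down to about 2 and under 1 at 90%. The true position cannot be fixed from the documents. Results through month 12 are sound if contact is complete to then. The ongoing-therapy imputation is a smaller, separate fault: it affects a descriptive duration, not the two curves.

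**What to change.** Change SAP wording only:

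- **5.6.5 and 5.6.7, main presentation.** Censor OS and TTNT administratively at 12 months from first injection and report 12-month rates with confidence intervals. The SAP plans no such rates for these endpoints, so this is an addition.
- **5.6.5 and 5.6.7, later data.** Keep the full curves and medians as descriptive. Beside them report length of follow-up by progression status, the number of progressed patients contacted beyond month 12, and whether that contact recorded subsequent therapy. Add a caution about informative censoring.
- **5.6.7, ongoing subsequent therapy.** Treat the duration as censored at last contact and summarise it by Kaplan-Meier, instead of imputing an end at the analysis cut-off.

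The cost is that late OS and TTNT figures lose prominence; none are discarded. Counting the contact period from progression would address the cause, but it needs a protocol amendment, and SAP Section 9 refers to termination of the study by the sponsor, so that is doubtful now.
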